7.4.6. Dose Modification Guidelines and Stopping Rules

In the event that any subject develops any AE \geq Grade 3 per CTCAE criteria version 5.0 in severity that is deemed related to treatment with study drug and not related to the underlying disease, the Principal Investigator should contact PTC's medical monitor to discuss dose modification options up to and including discontinuation of the administration of study drug.

In the event that any subject develops or is diagnosed with an allergy to vatiquinone or sesame oil after initiating treatment with study drug, administration of study drug will be discontinued.

In the event that any subject develops elevated INR \geq Grade 2 in severity ($>1.5 \times \text{ULN}$) per CTCAE criteria version 5.0 thought to be related to treatment with study drug, administration of study drug will be reduced to 66%. Should the INR toxicity not resolve to at least Grade 1 in severity within 2 weeks of the initial dose reduction, administration of study drug may either be further reduced or discontinued (Table 3).

Once a subject's dose is reduced due to elevated INR thought to be related to study drug administration, their dose should not be re-escalated.

Table 3: Dose Modification and Stopping Rules for Vatiquinone

Qualifying Event	Example Guidelines for Management		
	Recommendation	If Resolved to \leq Grade 1	If Not Resolved to \leq Grade 2 After 14 Days
INR \geq Grade 2 or $>1.5 \times \text{ULN}$ thought to be related to study drug and confirmed within 24-48 hours	Reduce dose by 1/3 from TID to BID Re-evaluate 7 days after dose reduction	Continue on-study at 2/3 dose.* *Once a subject is dose reduced, do not re-escalate.	Consider withdrawing the subject after consultation with the study medical monitor.

Abbreviations: AE, adverse event; DSMB, Data Safety Monitoring Board; INR, International Normalized Ratio; ULN, upper limit of normal

The investigator is responsible for decisions on dose holds, reductions, or interruptions for any clinically significant AE. The DSMB is responsible for determining dose modification or stopping actions for any other safety event.

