8.2. Sample Size Determination

It is planned to randomize 30 subjects per arm in this study. Sixty subjects (30 subjects in each treatment group) will provide a power of 81% to detect a 40% treatment difference with common standard deviation of 50% at a two-sided significance level of 0.05 based on the Wilcoxon Rank-Sum Test. The 40% treatment difference is based on 10% and 50% decrease in the placebo treatment group and PTC743 treatment group, respectively, for percent change from baseline in motor seizure frequency per 28 days.

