8.4.2. Analysis of Primary Efficacy Endpoints

Efficacy analyses will be based on the ITT population. Seizure frequency will be based on the number of seizures per 28 days, calculated as (the number of seizures over the time interval multiplied by 28) and divided by the number of days in the interval. Only “valid days” will be used in the calculations of seizures frequency per 28 days. A “valid day” is defined as the day where seizure counts information is present.

The percent change in the motor seizure frequency per 28 days in the double-blind period will be the primary efficacy endpoint.

For this analysis, first both the pre-randomization period motor seizure frequencies per 28 days as well as percent change in the double-blind period per 28 days will be rank transformed separately. The analysis of covariance will then be conducted on this rank transformed data with treatment, and stratifying factor (4 levels) and the ranked pre-randomization phase seizure frequency per 28 days as a covariate. P values will be computed using contrasts between active and placebo treatment groups.

Due to an expected irregular distribution of seizure frequency, median will be the primary statistic of interest for the primary endpoint. Hodges-Lehmann estimator and 95% confidence interval for this estimator will be displayed for understanding the treatment effect size.

A sensitivity analysis will be performed excluding all subjects with <25 days of valid days entered in the diary.

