2.1.3. Per-Protocol Population

The per-protocol (PP) population will include subjects in the ITT population who do not have any important protocol deviations leading to exclusion from the PP population.

The protocol deviations that may have major effect on efficacy which will lead to exclusion of the subjects from per-protocol population include:

- Subjects that had significant inclusion and exclusion criteria violations.
- Subjects that had protocol deviations which may impact effectiveness of study treatment.
- Subjects that received study treatment different from the randomized treatment throughout the double-blind period.
- Subjects with <80% of valid days entered in the seizure diary during the run-in period.

- Subjects with non-compliance to study drug administration with compliance <80% and >120%.
- Subjects with less than 80% compliance in the seizure diary of valid days entered in the diary during either run-in period or during double-blind period.
- Subjects who change anti-seizure medication or increase dose of anti-seizure medication not related to weight or begin/change in ketogenic diet during the study during double-blind period.
- Subjects that discontinued study treatment due to withdrawal, noncompliance, and death during the double-blind period.

All protocol deviations leading to exclusion from the PP population will be reviewed and approved by the study team prior to treatment unblinding. The list of PP population subjects will be finalized prior to treatment unblinding.

This population will be used as supportive efficacy analysis for the primary efficacy endpoint.

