3. GENERAL CONSIDERATIONS

3.1. Definition of Estimand for the Primary Objective

The primary estimand of the study is the percent change from baseline in frequency of observable motor seizures per 28 days during the double-blind period. The attributes of the primary estimand are defined in [Table 1](#).

Summary Measure:

The median of the variable of interest will be estimated for each treatment group. The difference in median of the variable of interest between two treatment groups will be estimated using Hodges-Lehmann estimator and 95% confidence interval (CI). The p-value will be computed from ranked ANCOVA detailed in [Section 5.1.2](#).

Table 1: Primary Estimands

Population	Variable	Intercurrent Events	Population-level Summary	Analysis
The population of subjects <21 years of age with genetically confirmed mitochondrial disease as defined by the protocol inclusion/exclusion criteria.	Percent change from baseline of motor seizure frequency per 28 days during the double-blind period.	
Rescue medication status: Study treatment will not be modified based on rescue medication status in line with a treatment-policy strategy.
 
Emergency room visits and hospitalization: The days which patient has emergency room visits, or is hospitalized, will not be excluded from the calculation of primary endpoint as long as the diary is available for such days in line with a treatment-policy strategy.
 
Changes in anti-seizure medications: Study treatment will not be modified and patient's will not be excluded as a result of changes in anti-seizure medications that are a medical necessity and in line with a treatment-policy strategy
 
Early termination or discontinuation: Data will be used as collected
	Treatment difference between vatiquinone and placebo in percent change from baseline to Week 24 will be estimated using the ANCOVA based on rank transformed data.	Primary analysis for primary efficacy endpoint

Abbreviations: ANCOVA, analysis of covariance

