4.6. Study Drug Compliance Based on Diary

Treatment compliance will be calculated as the percentage of the number of doses taken as recorded on diary out of what is expected to be taken in a period of interest,

$$\text{compliance} = \frac{\text{number of doses taken}}{3 \times \text{number of days in the period of interest (except on the day start first dose of OL period)}} \times 100\%$$

The number of days in the period of interest is defined as last dose date in the period of interest - first dose date in the period of interest + 1.

Last dose date during double-blind period is the same date as the start of the open-label period, and subject is expected to take 2 doses of the double-blind period medication and 1 dose of the open-label period medication. Denominator for the compliance calculation will be adjusted accordingly for subjects entered the open-label period.

The study drug compliance will be summarized by treatment for double-blind period, and by treatment sequence for open-label period, as well as for on-vatiquinone for Safety Population.

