4.7. Seizure Diary Compliance Based on Diary

Seizure diary compliance is defined as the percentage of number of days with a valid seizure diary entry out of number of days during the period of interest.

$$\text{compliance} = \frac{\text{number of days with seizure diary}}{\text{number of days in the period of interest}} \times 100\%$$

The number of days in double-blind period is defined as last dose date in the double-blind period - first dose date in the double-blind period + 1. For subject who entered the open-label period, the duration for the double-blind period is defined as: last dose date in the double-blind period - first dose date in the double-blind period. The handling is because the last dose date during double-blind period is the same as during start of open-label period, and the seizure diary will

not record the time of the seizure, all the seizures that occur on that day will be considered as during open-label period.

The number of days in open-label period is defined as last dose date in the open-label period-first dose date in the open-label period+1.

The seizure diary compliance will be summarized by treatment for double-blind period for ITT population.

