5.1.3. Sensitivity Analysis for Primary Endpoint

The following sensitivity analyses are planned.

1. The similar analysis as described for the primary analysis will be repeated using the PP population.
2. An analysis using the same model as described for primary analysis excluding all subjects with <80% of valid days entered in the diary in run-in period and/or the double-blind period.
3. An analysis using the same model as described for primary analysis excluding all subjects who change anti-seizure medication or increase dose of anti-seizure medication not related to weight or begin/change in ketogenic diet during the study.
4. An analysis using the same model as described for primary analysis excluding all subjects who discontinued due to withdrawal, noncompliance, and death during the double-blind period.
5. Analysis as described in the primary analysis will be performed for percentage change from baseline in the motor seizure frequency per 28 days during the double-blind period completers ie, all subjects that took medication until the end of the double-blind period as specified by the protocol and have >80% compliance for seizure diary, for ITT analysis sets.
6. Change from baseline of number of motor seizure per 28 days in the double-blind phase will be performed using the same model as described for primary analysis.
7. Analysis as described in the primary analysis will be performed for percentage change from baseline in the motor seizure frequency per 28 days during the last 12 weeks in the double-blind phase for ITT.
8. Analysis as described in the primary analysis will be performed for percentage change from baseline in the motor seizure frequency per 28 days during the last 4 weeks in the

double-blind phase for ITT. The last 4 weeks is defined as start 141st day post randomization until last dose date during the double-blind phase.

9. Descriptive summary will be performed for percentage change from baseline in the motor seizure frequency per 28 days during the double-blind phase for ITT population excluding subjects that had coronavirus disease of 2019 (COVID-19) during the double-blind phase.
10. Descriptive summary will be performed for percentage change from baseline in the motor seizure frequency per 28 days during the double-blind phase for ITT population excluding subjects with a do not resuscitate (DNR) order.

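### No planned sensitivity analysis tests robustness to what is unobserved after discontinuation or death, and the per-protocol drug-compliance formula can fail a fully adherent subject on a reduced regimen

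*SAP*

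**What the plan says.** **Primary handling.** SAP 3.1, Table 1, names a treatment-policy strategy for rescue medication, hospital or emergency visits, and anti-seizure medication changes. For early termination it says only "Data will be used as collected". SAP 3.2 and 3.7 rule out imputation as the general rule, and SAP 5.1.1 computes the rate on valid days alone.

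**Sensitivity handling.** SAP 3.1.1 groups death with withdrawal and noncompliance, and sends subjects who discontinue to separate sensitivity analyses. In SAP 5.1.3 these are item 1 (per-protocol set, which SAP 2.1.3 defines without them), item 4, run "excluding all subjects who discontinued due to withdrawal, noncompliance, and death during the double-blind period", and item 5 (double-blind completers).

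**Diary filter.** Protocol 8.4.2 states: "A sensitivity analysis will be performed excluding all subjects with <25 days of valid days entered in the diary". The SAP has an 80% rule instead, with this denominator in SAP 4.7: "The number of days in double-blind period is defined as last dose date in the double-blind period - first dose date in the double-blind period + 1". SAP 3.10 does not list the replacement as a change from the protocol.

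**Drug compliance.** SAP 4.6 defines compliance in words against the doses expected, and Protocol 8.4.6.3 against the amount that should have been taken. The SAP 4.6 formula divides by three times the "number of days in the period of interest (except on the day start first dose of OL period" (closing bracket omitted). Protocol 7.4.6, Table 3, has for a qualifying INR rise: "Reduce dose by 1/3 from TID to BID", without later re-escalation. SAP 2.1.3 removes from the per-protocol set subjects "with compliance <80% and >120" percent.

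**The concern.** The sponsor's own text expects deterioration in this population: rapid progression in the youngest (Protocol 4.2), increases in seizures (SAP 3.10), and DNR orders and death (SAP 5.1.3 and 3.1.1). A subject who stops on Day 40 enters the rank ANCOVA with the same weight as one followed for 168 days, and nothing after the stop counts.

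The analyses meant to examine this select on a post-randomisation event. If stops are unequal between arms and related to worsening, removing those subjects can push the comparison the same way as scoring them on their early days. Agreement between the primary analysis and items 1, 4 and 5 would then look like robustness without being evidence of it.

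The compliance formula is a separate and smaller matter. It can label a subject who followed the protocol as non-compliant and so change who is in the per-protocol set.

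**Working it through.** **1. The plan's own figure.** Protocol 8.2 says 30 per arm "will provide a power of 81% to detect a 40% treatment difference with common standard deviation of 50" percent, two-sided 0.05, Wilcoxon rank-sum; SAP 1.4 says 80%. Using the minimum Wilcoxon relative efficiency of 0.864:
- effective n = 30 × 0.864 = 25.92 per arm
- noncentrality = (40/50) × √(25.92/2) = 0.8 × 3.6 = 2.88
- noncentral-t power = 80.6%

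This matches both statements. No dropout allowance is stated.

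**2. What each item in SAP 5.1.3 does with an early stop or death.**

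| Item | Rule | Effect on early stops |
|---|---|---|
| 1, 4, 5 | per-protocol set; discontinued excluded; completers | removed by rule |
| 7, 8 | last 12 weeks; from day 141 | lost only if no diary days fall in the window |
| 2 | diary validity below 80% | kept if the diary is complete to last dose |
| 3 | anti-seizure medication or diet change | not removed as such |
| 6, 11 | absolute change; 4-week windows | kept as collected, or for the windows reached |
| 9, 10 | descriptive, without COVID-19 or DNR subjects | not removed as such |

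Three of the 11 items remove early stops by rule, two can lose them, and six do neither as such. None assigns an unfavourable value or varies the assumption about unobserved days.

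**3. Diary filter.** A stop at Day 40 with 38 entries scores 38/40 = 95% and stays in item 2, although 38/168 = 22.6% of the planned period was observed.

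**4. Illustration under no treatment effect.** Assumptions: 30 per arm; rank ANCOVA on treatment and ranked baseline, without strata; 4,000 runs; stopping correlated 0.5 or 0.9 with worsening; the pre-stop score either unrelated to the full-period change or correlated 0.5 with it. The stop counts are assumed. Entries are the chance of a significant result favouring vatiquinone (nominal 2.5%), as ranges over these settings.

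| Stops, vatiquinone vs placebo | As collected | Excluded | Worst rank |
|---|---|---|---|
| 6 vs 1 | 4–13% | 7–17% | below 1% |
| 4 vs 1 | 3–9% | 5–10% | about 1% or less |
| 3 vs 3 | 3–4% | 3–4% | below nominal |

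Exclusion does as badly as the as-collected analysis or worse. With the split reversed, as-collected and exclusion turn conservative and worst rank moves towards vatiquinone, because it responds to the imbalance in stops itself.

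**5. What worst rank costs.** Same model under the planning effect (means −10 and −50, SD 50, normal data), with events assigned without regard to outcome. Entries are the probability of a significant benefit.

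| Events, vatiquinone/placebo | As collected | Removed | Worst rank |
|---|---|---|---|
| 2/2 | 84% | 82% | 76% |
| 3/3 | 84% | 80% | 69% |
| 6/6 | 82% | 74% | 42% |
| 6/3 | 85% | 78% | 21% |

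**6. Compliance after a TID-to-BID switch.** With d TID days out of 168 and every directed dose taken:

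compliance = [3d + 2(168 − d)] / (3 × 168) = (336 + d)/504

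- d = 0: 336/504 = 66.7%
- d = 28: 364/504 = 72.2%
- d = 56: 392/504 = 77.8%
- d = 67: 403/504 = 79.96%
- d = 68: 404/504 = 80.2%

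Reaching 80% needs d ≥ 0.8 × 504 − 336 = 67.2, so 68 TID days. At 95% adherence it needs d ≥ 403.2/0.95 − 336 = 88.4, so 89. The one-dose adjustment for the day of entry to the extension moves the crossing by at most a day. With directed doses as denominator, the fully adherent subject scores 100%.

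**The case against.** A reader might infer that every sensitivity analysis deletes early stops, or that none tests robustness to anything. The table in step 2 shows otherwise: six items do not delete them as such, and items 3, 6, 7, 8 and 11 examine medication changes, outcome scale and time window. The gap is confined to what follows discontinuation or death.

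A reader might also infer that the primary analysis is biased towards vatiquinone. The documents do not establish a direction. SAP 2.2.1 runs the efficacy period to the last study visit for subjects who do not enter the extension, so stopping drug is not the same as leaving the study. Worsening recorded before a stop does count, and because the rate is per valid day, later days do not dilute it. The unequal splits in step 4 are chosen, not taken from the trial. These points stand; they limit the size of the concern but do not supply the missing analysis.

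Worst rank can fairly be called a composite strategy that answers a different question and costs power. That is right, and is why it belongs among the sensitivity analyses only.

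On compliance, the per-protocol set is supportive and its exclusions are reviewed before unblinding (SAP 2.1.3). Table 3 is headed as example guidelines, while the text of Protocol 7.4.6 speaks of a reduction to 66% without naming BID; a reduction by volume at three doses a day would not trigger the problem. Protocol 1.4.2 reports no coagulation changes attributed to vatiquinone in clinical studies, so few or no subjects may be affected, and a larger effect in the active arm cannot be assumed. All of this stands, but no exemption is written, and the formula still contradicts its own definition.

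**Conclusion.** The point holds in limited form. Deaths and early stops are scored on the days available, the three analyses aimed at discontinuation remove them, and the diary filter does not detect short follow-up. No planned analysis tests robustness to missing data after discontinuation or death, or treats death as unfavourable. How much this matters depends on the number, balance and cause of stops, which the documents do not give. It is small if stops are balanced and material if several more occur in one arm and are related to worsening.

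The SAP 4.6 formula is wrong as written. It affects only the per-protocol analysis, only subjects whose daily dose count is reduced, and at full adherence only those switched after 67 or fewer TID days. The number of such subjects is unknown.

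The per-protocol compliance limits, which as worded no subject can meet together, are a clerical slip: Protocol 5.4 makes the intended range plain.

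**What to change.** 1. **SAP 5.1.3.** Add to item 4, or put in its place, the same rank ANCOVA on the full ITT set with deaths and discontinuations for adverse event or lack of efficacy given the worst ranks. Fix the classification of reasons before unblinding. Label it a sensitivity analysis and leave the primary unchanged. Cost: one table and no new data, since reasons are already recorded (Protocol 6.2). Downside: it is conservative and loses power, as step 5 shows.
2. **SAP 4.6.** Use as denominator the doses prescribed for each subject, including protocol-directed reductions, and reconcile the formula with Protocol 7.4.6, where the text and Table 3 also need to agree. No view is taken here on the dosing rule. Cost: a wording change and one derivation.
3. **SAP 2.1.3, editorial.** Replace the conjunction so that the limits read <80% or >120%.
4. **SAP 3.10.** List the dropped <25-valid-day analysis as a change from the protocol. It need not be reinstated, being itself a post-randomisation exclusion if read as applying to the double-blind diary; Protocol 8.4.2 does not state the period.

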5.1.4. Subgroup Analysis

Median and corresponding 95% CI of percent change from baseline of motor seizure frequency per 28 days will be summarized for subgroups below for double-blind period for ITT population:

- Age group (<8 years old vs ≥ 8 years old)
- Sex (Male vs Female)
- Race (White vs Other)
- Region (United States vs Rest of the World)

5.2. Secondary Endpoint(s) Analysis

5.2.1. Key/Confirmatory Secondary Endpoint(s)

The key secondary efficacy endpoints of the study are as follows:

- Number of disease-related hospitalization days
- Occurrence or recurrence of status epilepticus

For the key secondary endpoints, if subject is without any events at baseline, ie, no hospitalization or status epilepticus at baseline, then subject will be considered as having 0 events at baseline.

5.2.1.1. Number of Disease-Related Hospitalization Days

Number of disease-related hospitalization days per 28 days will be calculated as the total number of disease-related hospitalization days multiplied by 28 and divided by the total number of days in the interval.

Disease related hospitalization is defined as any hospitalizations occurring as the consequence of an AE or SAE during the study period that is related to the subject's disease state or baseline conditions of the subject and lack of alternative explanation for the event. All the hospitalization events will be reviewed, classified as disease-related or not and agreed upon prior to the study unblinding.

The change from baseline in number of disease-related hospitalization days per 28 days during the double-blind period will be compared between the treatment groups using Wilcoxon rank-sum test for ITT population.

The number and the change from baseline in number of disease-related hospitalization days per 28 days during the double-blind period will be summarized descriptively for ITT population. Number of disease-related hospitalization days will be tabulated by frequency and percent as well for double-blind period, respectively, for ITT.

In addition, the change from baseline in number of disease-related hospitalization days per 28 days will also be summarized descriptively for the following subgroups for double-blind period for ITT population.

- Age group (<8 years old vs ≥ 8 years old)
- Sex (Male vs Female)
- Race (White vs Other)
- Region (United States vs Rest of the World)

